HRP-503B – BIOMEDICAL RESEARCH PROTOCOL (2017-1)

Protocol Title: Preliminary Effectiveness of Remotely Monitored Blood Alcohol Concentration Device as Treatment Modality

Principal Investigator: [name].

Version Date: June 1, 2020

(If applicable) Clinicaltrials.gov Registration #: NCT04380116

INSTRUCTIONS

This template is intended to help investigators prepare a protocol that includes all of the necessary information needed by the IRB to determine whether a study meets approval criteria. **Read the following instructions before proceeding:**

- 1. Use this protocol template for a PI initiated study that includes direct interactions with research subjects. Additional templates for other types of research protocols are available in the system Library.
- 2. If a section or question does not apply to your research study, type "Not Applicable" underneath.
- 3. Once completed, upload your protocol in the "Basic Information" screen in IRES IRB system.

SECTION I: RESEARCH PLAN

1. **Statement of Purpose:** State the scientific aim(s) of the study, or the hypotheses to be tested. The purpose of the current study is to evaluate the usage and acceptability of the Soberlink's blood alcohol concentration (BAC) unit in collaboration with Aware treatment to assess increased sobriety within patients suffering from alcohol use disorder (AUD).

The specific AIMS will be:

- 1) To determine the effectiveness of Soberlink's ability to increase abstinence
- 2) To evaluate the impact of Soberlink's device on the participant based on their quality of health and sobriety.
- 3) To evaluate the extent to which need for higher levels of follow-up care and treatment is reduced for individuals who have had access to the Soberlink device.
- 2. **Probable Duration of Project:** State the expected duration of the project, including all follow-up and data analysis activities.

The duration of the time of the study will be two years to complete. This will include (as seen on Figure 1) time for IRB approval and recruitment, randomization and completion the study, follow-up and lastly analysis with dissemination.

[figure not shown]

Figure 1: Overview and Timeline

3. **Background:** Describe the background information that led to the plan for this project. Provide references to support the expectation of obtaining useful scientific data.

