Patients assigned to the Soberlink-Aware condition will receive a 30-minute orientation to the Soberlink, including an initial their first administration of the BAU. Participants will learn the following:

- 1. The Soberlink System consists of a wireless Breathalyzer that uses a professional grade fuel cell sensor to detect alcohol levels at an accuracy of +/-.005 BAC.
- 2. The device also has an embedded camera and uses Facial Recognition software to automatically identify the client at the end of the test.
- 3. The participant will have a set testing schedule that consists of a minimum of 2 tests per day. The participant will have a test window of 2 hours with a Late window of 1 hour.
- 4. When the participant blows into the Soberlink device, it will capture the BAC level while the embedded camera takes a photo of the participant during the test

The breathalyzer device uses fuel cell technology to detect BAC, is handheld, and includes an embedded camera. It uses wireless technology to send the data in real-time. The cloud-based monitoring system includes a scheduler that automatically tracks scheduled tests and sends reminders to the client for testing. Retesting is automatically scheduled if a positive test is received or if a client's identity cannot be verified. The device locks out for 15 minutes to ensure alcohol evaporates before the next test. Facial Recognition software ensures identity is

IRB# 2000027787

approved or declined in real-time. Artificial intelligence is used to report on testing and Green, Yellow and Red visual icons are used in all reporting to identify events.

All individuals in group 1 will be required to complete two BAC's per day. A testing window will be scheduled with each individual between 7am to 9am (morning BAC) and 8pm to 10pm (evening BAC). During the testing window, all individual in this group can provide the BAC at any time within the window, all tests performed outside the window will be recorded but counted as unscheduled test on the BAC spreadsheet. All participants can opt in to receive a text-reminder sent by Soberlink's automated server to remind the patient about their morning and evening BACs.

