We are planning to assess a broad range of subject characteristics, process measures and treatment outcomes over the 3-month trial and at the 6 week post treatment follow-up (See Table 1). Baseline assessments are designed to ensure that patients meet eligibility criteria and that important predictor variables such as cognitive impairment are assessed. Baseline measures include evaluation and understanding of the extent of the AUD issue from a several different vantages points. Primary outcome measures include reductions in days per week of use and negative BAU screens for alcohol. Monthly assessments will take approximately 30 minutes and monthly and follow-up's 45 minutes. Patients will be paid \$10 for the baseline and monthly assessments, \$25 for follow-up assessments (up to \$65 total).

active alcohol use disorders.

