Table 1. List of Assessments Screening & Baseline Assessments a) Generalized Anxiety Disorder (GAD-7) will be used to assess for generalized anxiety The Structured Clinical Interview for DSM-V (SCID) will be used to assess lifetime and current DSM- V substance use and Axis I and II psychiatric disorders ¹⁸¹ and screen patients for psychiatric eligibility. c) Patient Health Questionnaire (PHQ-9) will be used for depression symptoms for the past 2 weeks. d) Substance Use History will assess frequency, intensity and duration of use and route of administration of drugs. e) Alcohol Abstinence Self-Efficacy Scale will evaluate the participant's beliefs of alcohol usage. Outcome Measures. a) Soberlink (BAC): sensor to detect alcohol levels at an accuracy of +/-.005 BAC. BAC is established by the manufacturer based on predetermined cut off points b) The Time Line Follow Back (TLFB), administered by research administer onto a secure webserver. Will be used to collect self-reported frequency, quantity and route of administration of prescription opioids, cocaine, alcohol and other drugs use during the preceding 30 days, and use 185-187 Quality of Life Scale is a self-directed survey that assess the quality of life of the individual. d) Soberlink Use Survey is a self-directed survey that evaluates the effectiveness of the device. e) The Drug Risk Response Test (DRRT) ^{189,190} is a role-playing assessment of coping responses to drug use risk situations, and takes 8-10 minutes to complete. The instrument is composed of six audio-taped scenarios. Patients are instructed to imagine that they are in the situation and provide a detailed account to how they would respond to that situation. Patient accounts are recorded and scored by trained evaluators. The instrument provides 4 measures: the number of coping responses, the number of activities per response, the quality of the best response and the

Data monitoring procedures involve an organizational structure of clearly defined tasks assigned to all research personnel involved in the conduct of this study. The organizational structure used to ensure quality of data in this project include: 1) extensive training and close supervision of research assistants in data collection;

f) AUDIT C- is brief alcohol screen that reliably identifies patients who are hazardous drinkers or have

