13. **Statistical Considerations:** Describe the statistical analyses that support the study design. A sample size of 110 would provide >80% power (α = .05) to detect a medium to large effect size (d= .65) and allow to fully evaluate gender differences. Greater power is provided by the repeated measures GEE and LMM analysis for the primary outcomes of BAC screen negative for alcohol drugs and days/month of self-reported illicit drug use. Sample size calculations for LMM are dependent on the number of repeated events, the retention rate, and the interclass correlation, in addition to the alpha level, the expected effect size, and the statistical power 198. The current randomized trial would provide estimates to guide a power analysis for a large Stage II study. Statistical procedures and models for analyzing data have been selected according to the research hypotheses being investigated and the types of data available. We will use α < .05, but will use appropriate corrections for multiple tests. Statistical analyses will be conducted on an intention-to-treat sample using SPSS. Using chi square and t-tests, we will first conduct preliminary analyses of the adequacy of the randomization procedure, the comparability of baseline measures for the two groups, and the possible need for covariates in the analyses of treatment outcome data.

SECTION II: RESEARCH INVOLVING DRUGS, BIOLOGICS, RADIOTRACERS, PLACEBOS AND DEVICES

ft
his
section
(or one
of its part
s. A or B
() is not
applicable.
check o
ff N/A
and de
lete the
rest of th
e section.

A.	RADIOTRACERS ⊠N/A	
1.	Name of the radiotracer: Write here	
2.	Is the radiotracer FDA approved? □YES	□NO

- If NO, an FDA issued IND is required for the investigational use unless RDRC assumes oversight.
- 4. **Background Information:** Provide a description of previous human use, known risks, and data addressing dosage(s), interval(s), route(s) of administration, and any other factors that might influence risks. If this is the first time this radiotracer is being administered to humans, include relevant data on animal models.

Check one: □IND# Write here or □RDRC oversight (RDRC approval will be required prior to use)

Write here

3.

4. **Source:** Identify the source of the radiotracer to be used. *Write here*

5. **Storage, Preparation and Use:** Describe the method of storage, preparation, stability information, method of sterilization and method of testing sterility and pyrogenicity.

Write here

R	DRUGS/BIOLOGICS

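### A negative screen at two fixed, known times a day shows no detectable alcohol at those times, not abstinence, so Group 1's breath-based abstinence can only err upwards

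*Combined protocol and SAP*

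**What the plan says.** The first aim in Section I, item 1 (Statement of Purpose) is "To determine the effectiveness of Soberlink's ability to increase abstinence".

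The testing rules are in item 4 (Research Plan), under Orientation to Soberlink. "All individuals in group 1 will be required to complete two BAC's per day", and the times are fixed: "A testing window will be scheduled with each individual between 7am to 9am (morning BAC) and 8pm to 10pm (evening BAC". Participants are taught the schedule: "The participant will have a set testing schedule that consists of a minimum of 2 tests per day". They are also told: "The participant will have a test window of 2 hours with a Late window of 1 hour". Tests outside the window are kept but labelled unscheduled. Automatic retests follow only a positive result or a failed identity check. No test at a random or intermediate time is planned.

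Under Assessments in item 4, "Primary outcome measures include reductions in days per week of use and negative BAU screens for alcohol". Item 13 (Statistical Considerations) likewise names the "primary outcomes of BAC screen negative for alcohol drugs", beside a self-reported count of days of use. Table 1 gives the cut-off only by reference: "BAC is established by the manufacturer based on predetermined cut off points". Table 1 also lists the TLFB, which covers alcohol over the preceding 30 days. Group 2 completes the same surveys at the same times but has no device.

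**The concern.** A breath test measures the alcohol present when it is taken. It looks back only as far as alcohol from an earlier episode is still above the cut-off. With two tests at known times, an episode can start and clear between them, and every scheduled test is then negative.

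The plan does not say what a negative screen stands for. It has no rule that turns tests into abstinent days and no comparison of breath results with the TLFB. Because Aim 1 is abstinence and the negative screen is a primary outcome, a high share of negative screens in Group 1 is likely to be reported as evidence of abstinence. Continued drinking between tests could produce the same figure.

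**Working it through.** The plan gives no between-test interval, detection limit or detection rate, so there is no figure of its own to reproduce on this point. The sample size is not affected.

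**Step 1. Time between tests (from the documents).**
- Morning to evening: shortest 20:00 − 09:00 = 11 h; longest 22:00 − 07:00 = 15 h.
- Evening to next morning: shortest 22:00 to 07:00 = 9 h; longest 20:00 to 09:00 = 13 h.
- Overall 9-15 h. With the late hour (windows to 10:00 and 23:00), the gaps are 10-16 h by day and 8-14 h overnight, so 8-16 h overall.

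**Step 2. Detection model (assumptions, not in the documents).** There is one episode, with linear elimination β of 0.010-0.025 per hour and a cut-off c of 0.005-0.02. Test times are uniform within the windows and peak time is uniform over 24 hours. Only tests after the peak count. The central case is β = 0.015 and c = 0.02.

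Look-back after the peak is L = (peak − c)/β. While L is no longer than the shortest gap (9 h), the share of episodes detected is 2L/24. Beyond that the look-backs overlap, and the share comes from simulation (200,000 draws).

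| Peak | Central L | Detected, central | Detected, range |
|---|---|---|---|
| 0.05 | 0.03/0.015 = 2.0 h | 4/24 = 17% | 10-38% |
| 0.08 | 0.06/0.015 = 4.0 h | 8/24 = 33% | 20-63% |
| 0.12 | 0.10/0.015 = 6.7 h | 13.3/24 = 56% | 33-93% |
| 0.16 | 0.14/0.015 = 9.3 h | 78% (simulated) | 46-100% |
| 0.20 | 0.18/0.015 = 12 h | about 95% (simulated) | 60-100% |

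The limits for 0.08 come from (0.08 − 0.02)/0.025 = 2.4 h, so 4.8/24 = 20%, and (0.08 − 0.005)/0.010 = 7.5 h, so 15/24 = 63%.

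**Step 3. Count tests taken while the level is rising.** With an assumed linear rise over 2 hours to 0.08, the level is above 0.02 for 2 × (1 − 0.02/0.08) = 1.5 h before the peak. Detection becomes 2 × (4.0 + 1.5)/24 = 46% in the central case (32-78% over the range).

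**Step 4. Vary the time of drinking (peak 0.08).**
- Peak at 5-10pm: 75% detected (48-80%) on tests after the peak; 94% centrally with a 2-hour rise.
- Peak at 10am-5pm: 4% (0-50%) on tests after the peak.
- Peak at 10pm-2am: 0% (0-37%) on tests after the peak; 14% centrally with a 2-hour rise.

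In the central case, a peak at 10pm must reach 0.015 × 10 + 0.02 = 0.17 to be positive at 8am.

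**Step 5. Effect on a reported rate (illustration).** Suppose a participant drinks on 30% of days to a peak of 0.08. On the 33% figure, 0.30 × 0.33 = 10% of days have a positive test. At two tests a day that is 5% of tests, so 95% of screens are negative. On the 46% figure, 0.30 × 0.46 = 14% of days are positive and about 93% of screens are negative.

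**Step 6. Cross-check by number of drinks.** A second model used 14 g drinks at two per hour, an 80 kg man and a 65 kg woman, and the same β and cut-off ranges. With start time uniform over 24 hours, all scheduled tests miss 40-96% of two-drink sessions, 9-87% of three-drink sessions and 0-61% of six-drink sessions. Two drinks begun straight after a test are missed in every scenario.

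**The case against.** The strongest reply is that the size is unknown and may be small where it matters. Participants have diagnosed alcohol use disorder, so heavy episodes are relevant, and at a peak of 0.20 the tests detect 60-100%. Early-evening drinking, which falls just before or during the evening window, is mostly caught. The three-drink range of 9-87% shows how far any figure depends on assumptions. All of this stands. A reader might infer that most moderate drinking goes undetected, but the documents cannot establish that.

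A reader might also describe the 9 to 15 hours as unmonitored. That is too strong: it is the time between tests, and each test looks back some hours.

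It can further be said that the plan labels the outcome a negative screen rather than abstinence, and pairs it with self-reported use, which covers drinking at any hour. That is correct, but the plan does not link the two measures. Item 13 describes the self-report outcome as illicit drug use, which leaves the breath screen as the only primary outcome there that names alcohol.

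The Research Plan mentions a pilot at the site with little reactivity among device users. No data are given, and reactivity does not bear on what a test can detect. Equally, nothing in the documents shows that participants will move their drinking into the gaps. The schedule makes that possible, no more.

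Twice-daily testing is a reasonable compromise on burden in a preliminary trial. The point concerns what the result is taken to mean, not how often tests are done.

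**Conclusion.** The point holds in this form: a negative screen shows no detectable alcohol at that test, and through missed episodes Group 1's breath-based abstinence can only be too high. The direction and the 9-15 h (8-16 h) intervals follow from the documents and from how a breath test works. The size rests on assumed elimination rates, cut-offs, peaks and drinking times, and runs from slight for heavy or early-evening drinking to severe for light or late-night drinking.

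A reader might infer that the error favours the device in the trial comparison. The documents do not support that. Group 2 has no breath tests, so there is no between-arm breath contrast to bias; the error is confined to Group 1's absolute rate. For the same reason, the breath outcome cannot answer Aim 1 between arms. The change is worth making because data already planned for both arms give a better answer.

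**What to change.** In item 4 (Assessments) and item 13:

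1. Answer Aim 1 between arms with TLFB alcohol-use days, which both arms complete. Item 13 should name alcohol in the self-report outcome.
2. Report the breath outcome descriptively, for Group 1 only, as no alcohol detected at scheduled tests. State the cut-off as a number and how late, unscheduled and missed tests are scored.
3. For any Group 1 breath-based abstinence figure, classify each day as follows:
   - drinking, if any breath test (scheduled, late, unscheduled or retest) is positive or the TLFB reports alcohol;
   - alcohol-free, only if both scheduled tests are negative and the TLFB reports none;
   - undetermined otherwise, with a sensitivity analysis.
4. Record TLFB alcohol use by day; Table 1 does not say that it is. The 30-day recall also leaves 42 − 30 = 12 days of the six-week follow-up uncovered, so say how those days are handled.
5. Report the share of TLFB drinking days on which all tests were negative. Treat it as a lower-bound check on missed drinking, since drinking hidden from the tests may also go unreported.

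The testing schedule and sample size need not change. The cost is revised wording, day-level TLFB entry and a merge of two data sets. The downside is a less favourable Group 1 abstinence figure.

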Alcohol dependence (AD) has been characterized as a chronic disorder that presents an enduring vulnerability to relapse. Unfortunately, AD treatment is commonly delivered as a series of acute care sessions (Etheridge, Craddock, Dunteman, & Hubbard, 1995; McLellan, Lewis, O'Brien, & Kleber, 2000), which means that individuals seeking treatment often face the challenge of maintaining sobriety upon returning to the same environment where they had struggled with alcohol dependence previous to seeking treatment. Studies have shown that 40%–60% of patients treated for alcohol problems relapse within 3 months, and this rate increases to 70%–80% within 12 months (Bradizza, Stasiewicz, & Paas, 2006; McLellan et al., 2000; Witkiewitz & Marlatt, 2004). medical costs associated with alcohol use disorders (AD) are over \$120 billion per year, until very recently, there has been relatively little involvement of physicians or other general healthcare providers in the treatment of AUDs (Sacks et al., 2015). By convention, most contemporary AUD treatment has been delivered outside mainstream healthcare by specialty "treatment programs" that are time-limited by insurance restrictions and highly structured to deliver a standardized "program" of care (McLellan et al., 2005; Foll et al., 2009).

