Individuals who miss two consecutive BAC's will be followed up by either Research Assistant or the PI. Individuals who miss four consecutive BAC's without contact of the PI or the research assistant will be temporarily hold unless the individual has expressed thoughts of leaving the study prematurely. Missing more than six consecutive BACs without communication will result in termination from the study by the PI. A pilot study contacted at Aware prior to the PI being involved demonstrated little reactivity or premature departure for those who had access to the Soberlink device.

Aware/Group 2:

This group will not receive access or training to Soberlink device, however they will be recruited to complete the same set of surveys at the same time intervals (See Figure 2). Upon completion of the surveys, the participants in group 2 will be paid, and told reminded the subsequent follow-ups. Reminder emails (see attached reminder emails) will be sent out the day before, and the day of the 1 month, 2 month and 3 month evaluations. Subsequent phone calls will be made by the research assistant to the participant if they have missed their evaluation. The estimated time of the process will take under 30 minutes to complete.

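### The missed-BAC rule ends study participation in Group 1 only, and nothing visible keeps the surveys going afterwards, so self-reported days of use could be lost selectively in one arm

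*Combined protocol and SAP*

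**What the plan says.** The rule stands in Section I.4, in the Group 1 procedures under Orientation to Soberlink: "Missing more than six consecutive BACs without communication will result in termination from the study by the PI". Two earlier steps precede it. First, "Individuals who miss two consecutive BAC's will be followed up by either Research Assistant or the PI". Then four consecutive misses without contact lead to a temporary hold.

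The testing duty falls on one arm: "All individuals in group 1 will be required to complete two BAC's per day". On Group 2 the plan says: "This group will not receive access or training to Soberlink device, however they will be recruited to complete the same set of surveys". Both arms share one survey schedule.

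For a missed survey, the Group 1 and Group 2 descriptions give the same response: "Subsequent phone calls will be made by the research assistant to the participant if they have missed their evaluation".

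Under Assessments, "Primary outcome measures include reductions in days per week of use and negative BAU screens for alcohol". Table 1 describes the TLFB as self-report covering the preceding 30 days. Section I.13 plans GEE and LMM on an intention-to-treat sample. It names no rule for missing outcomes or for terminated participants.

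On how often people leave, the only information is that a pilot at the site "demonstrated little reactivity or premature departure for those who had access to the Soberlink device". No rate is given.

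**The concern.** The two arms have the same survey schedule and the same response to a missed survey, but only one has an additional way out of the study. A Group 1 participant who is silent for about three and a half days can be terminated. A Group 2 participant who is silent for as long triggers nothing until a survey is missed, and then gets a call.

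Device results exist only in Group 1, so of the two primary outcomes only self-reported days of use can be compared between the arms. If prolonged silence is related to drinking, the rule could remove that outcome selectively from one randomised arm. This would weaken the comparison and the estimates that Section I.13 wants to carry into a Stage II power calculation.

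**Working it through.** **1. Timing.** More than six misses means the seventh. At two tests a day, 7 / 2 = 3.5 days.

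**2. Who can be reached by each provision.**

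| Event | Group 1 | Group 2 |
|---|---|---|
| Missed survey | phone call | phone call |
| Seven missed BACs, no communication | termination from the study | cannot occur |
| Surveys/TLFB after termination | not stated | not applicable |

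**3. The plan's own figure.** Section I.13 gives 110 participants, d = 0.65, α = .05 and power above 80%. With 55 per arm and a two-sided test (both assumed), power = Φ(0.65 × √(55/2) − 1.96) = Φ(1.449) = 92.6%, or 92.2% by the noncentral t. The claim reproduces. Losing 20% of Group 1 (44 against 55) leaves 88.9%, and power stays at or above 80% down to 30 in Group 1. Lost precision is not the issue. Selective loss is.

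**4. What determines bias in a mean.** If a share q of Group 1 is lost, and those lost differ from those retained by D standard deviations in days of use, the observed Group 1 mean shifts by −q × D. At q = 20%:
- D = +1.0 gives −0.20 SD, favouring Soberlink.
- D = −0.5 gives +0.10 SD, against it.

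The documents give neither q nor D.

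**5. Binary illustration, not the planned GEE/LMM.** Assumptions: 55 per arm, no true effect, one relapse endpoint, available cases only, pooled two-proportion z-test at two-sided .05 without the multiplicity correction that Section I.13 promises, 400,000 simulated trials. The 50% relapse rate is the middle of the 40–60% that Section I.3 gives as the share "of patients treated for alcohol problems relapse within 3 months". That is general background and may be high for this programme. The share of Group 1 relapsers lost, f, is assumed throughout.

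Observed relapse = r(1 − a_r) / [r(1 − a_r) + (1 − r)(1 − a_n)], where r is the relapse rate and a_r and a_n are the shares of relapsers and non-relapsers lost.

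Only Group 1 relapsers lost, r = 50% (27.5 relapsers expected per arm):

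| f | People lost | Observed relapse, Group 1 vs Group 2 | False-positive rate |
|---|---|---|---|
| 0 | 0 | 50% vs 50% | .045 |
| 10% | about 3 | .45/.95 = 47.4% vs 50% | .058 |
| 20% | about 6 | .40/.90 = 44.4% vs 50% | .088 |
| one third (assumed extreme) | about 9 | .333/.833 = 40.0% vs 50% | .172 |

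At 30% relapse, f = 10%, 20% and one third give .057, .081 and .147. At 20% relapse they give .055, .072 and .120.

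Offsets at f = one third, r = 50%:
- Group 1 non-relapsers lost at half that rate: .084.
- Group 2 relapsers lost at half that rate: .084. This is also the case where half of those terminated would have missed the survey anyway.
- Both: .333/.750 = 44.4% vs .417/.917 = 45.5%, rate .052.
- Both, plus one twelfth of Group 2 non-relapsers: 44.4% vs 47.6%, rate .061.

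Cases with no bias or the opposite sign:
- Equal loss of relapsers and non-relapsers gives no bias.
- Group 1 non-relapsers lost at 1/3 and relapsers at 1/6: .417/.750 = 55.6% vs 50%, against Soberlink.
- Missing counted as drinking: no bias if only relapsers leave. If 10% of Group 1 non-relapsers leave, .50 + .50 × .10 = 55% vs 50%, against Soberlink.

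**The case against.** **The rule is narrow.** It needs an unbroken run of misses and no communication, after staff follow-up at two misses and a hold at four. Those terminated are hard to reach by definition, and some would not have answered surveys anyway. The pilot remark points to few departures. All of this stands and limits the likely size. A remark without a rate cannot exclude a problem.

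**The planned models use partial records.** This also stands. Surveys completed before termination enter the GEE or LMM, so the binary figures do not carry over to the planned analysis in either direction. Someone terminated after a survey that recorded drinking leaves that information behind. Someone terminated before it leaves only earlier surveys. The models rest on missing-data assumptions that the plan does not state and that are doubtful if silence reflects drinking.

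**Intention-to-treat is already promised.** That settles who is analysed. It does not collect the missing surveys.

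**No text says that surveys stop.** True, and Figure 2 and the consent pages are not visible. But termination from the study, read as written, ends participation, and nothing visible says otherwise.

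A reader might infer that the trial is biased toward Soberlink, or that a 17% false-positive rate is the upper end of a plausible range. Neither is supported. No section links silence to drinking, and 17% needs an assumed one-third loss of relapsers, no other loss and a single binary endpoint. A reader might also see a conflict with the withdrawal provision in Section I.11. None is shown: that provision is clinical, covers both arms and contradicts nothing here.

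**Conclusion.** The point holds as a design weakness that is cheap to remove. The plan as written contains an exit from the study that can operate in one randomised arm only. No visible provision keeps collecting the one primary outcome that both arms share. Direction and size cannot be determined, and the effect may be nil.

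Under the binary assumptions above, one-sided loss of 10% or 20% of Group 1 relapsers gives a false-positive rate of about 6% or 9%, against about 5% with no loss. The 17% at one third is an assumed extreme, and partial offsetting losses bring it back to 5–8%. These figures show the mechanism. They do not estimate the error rate of the planned GEE/LMM. Confidence is medium, because the termination share is unknown and some pages are not visible.

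**What to change.** In Section I.4, separate the end of device testing from leaving the study. The device-testing rule and every clinical withdrawal or safety decision stay as they are. State that participants whose device testing is ended are still offered the month 1, 2 and 3 surveys with TLFB and the 6-week follow-up, with the same reminders and calls as Group 2, unless they withdraw consent. Report terminations and missing surveys by arm. Optionally, add to Section I.13 one simple sensitivity analysis for missing days of use, for example with missing counted as drinking. As shown above, that analysis can itself tilt against Soberlink, so it belongs beside the main analysis rather than in its place.

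The cost is a short amendment, consent wording and extra calls. Gift cards come to at most 3 × $10 + $25 = $55 per retained participant, which is $165 for 3 people or $495 for 9. This stays within the $65 per person in Section VI.2. Some unreachable participants will still be missing, so any bias is reduced rather than removed. In the extreme one-third case, recovering 25%, 50% or 75% of those terminated lowers the illustrative rate from 17% to about 11%, 8% or 6%. The recovery rate is unknown.
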